**Inclusion criteria:**

- Established diagnosis of epilepsy, characterized by focal seizures with suspected or documented localization in the temporal lobe. All participants will have active epilepsy that requires treatment with anticonvulsant medication.
  - Although it is not necessary to be seizure free, a seizure baseline period will be established in the 60 days prior to enrollment into the study.
  - Current regimen of anticonvulsant drugs must have been stable for 30 days prior to entry into the study.
- No episodes of seizure clusters of status epilepticus within 30 days prior to entry into the study.
- Established symptoms of anxiety with functional impairment.
- Baseline behavioral criteria for inclusion will include subscale scores above the norm for age and gender on one of the following:
  - Pediatric Anxiety Rating Scale (PARS).
  - Multidimensional Anxiety Scale (MASC)
- Male or female participants equal to or above age 6 and below age 18 at the start of the study. No exclusion will be made on the basis of gender or minority status.
- Good general health as determined by medical history and physical examination.
- Ability to swallow pills (participant will receive pill swallowing instruction if necessary). The medicine may be cut into pieces and/or mixed with applesauce.
- If female of childbearing age, a negative urine or serum pregnancy test must be established or assured at baseline. Additionally, the participant must agree to use abstinence or appropriate contraception methods or be otherwise incapable of pregnancy for the duration of the study. Pregnancy test results will be shared with parent or guardian. Pregnancy status (or prevention) and abstinence or contraception methods will be addressed

throughout the study for females of childbearing age as well as for post-pubertal males.

- Previous subjects who failed at any point to meet continuation criteria and withdrew early may be considered for re-enrollment by the PI on a case-by-case basis.
- Participant or legal caregiver capable of providing informed consent and fully capable of monitoring the subject's disease process and compliance with treatment.

#### **Exclusion criteria:**

- Previous allergic or hypersensitivity reactions to Onfi® or benzodiazepines
- Active substance abuse or dependence within 30 days of enrollment
- DSM-V diagnosis of psychotic illness or imminent risk of harm to self or others.
- Current use of antidepressants
- Current standing use of benzodiazepines (except as "rescue" medicine)
- Serious or unstable medical or neurologic conditions such as HIV, liver or kidney disease, cancer or diabetes.
- Participation in a previous experimental drug study within 30 days of baseline visit.
- Estimated IQ<70 as indicated by initial clinical assessment (rendering rating scales invalid)
- Insufficient capacity of caregiver or legal guardian to understand and appropriately consent for study procedures

#### **Statistical Analysis Plan**

Change from baseline will be analyzed statistically to test the main study hypotheses--that Onfi® has a dual role of improving both behavioral/psychiatric status, namely anxiety symptoms, as well as seizure control, in patients with epilepsy.

Outcome measures will encompass behavioral and neurologic status. The primary outcome variable will be Clinical Global Assessment of Functioning Improvement from baseline. CGI ratings will be attributed both to neurological status including seizure control, as well as behavioral status. CGI-Improvement ratings of a 1 or 2 (on a 7 point scale) will be considered positive responses. Paired student's t-tests will be used to compare baseline and study endpoint ratings for response versus non-response.

Secondary outcome measures will include changes from baseline in overall and subscale ratings of the Pediatric Anxiety Rating Scale (PARS), Multidimensional Anxiety Scale (MASC), and the Quality of Life in Epilepsy Scale. Positive outcomes will be defined as 10% score reduction or scores that drop below threshold of clinical significance. Paired student's t-tests will be used to compare baseline and study end outcomes for each measure.

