## Abstract

Certain mood stabilizer/anticonvulsant medications may be better suited for epilepsy with comorbid psychiatric illness. Many anticonvulsants are broad-spectrum and are well established as improving outcome for epilepsy as well as for behavioral disorders. The intuitive choice for treatment in patients with such comorbidity would be medications with an established track record in successfully treating both conditions independently. Benzodiazepines are a mainstay of anxiety treatment as well as for epilepsy treatment.

Given its unique molecular structure, clobazam (Onfi®) is an example of a medication that theoretically could serve a “dual role” in terms of treating epilepsy as well as anxiety disorder. Anxiety is prominent in children and adolescents with epilepsy although the evidence base is underdeveloped.

This study would assess the utility of clobazam, which may represent a more effective and better tolerated treatment option for the numerous patients with seizure disorders who also have anxiety. This study is an investigator initiated proposal submitted by the PI and is a prospective open-label clinical trial of 20 children and adolescents with epilepsy. The assessments include standardized questionnaires widely used in clinical practice as well as structured psychiatric diagnostic tools. Overall, this study will contribute valuably to an understudied patient population and add key information to the evidence base that potentially will make an immediate clinical impact.

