## Overview of Study Design

This study is an open label, adjunctive, proof of concept, pilot clinical trial. Prospective participants will be identified from chronic epilepsy clinical populations of Johns Hopkins Hospital and Kennedy Krieger Institute. Pediatric participants will be considered for the study if neurologic status suggests the need for additional treatment, and behavioral characteristics are clinically significant. All participants will receive active treatment, involving flexible dose titration of clobazam and will be monitored for a period of four months. The study will be monitored and overseen by the Johns Hopkins Hospital Institutional Review Board.

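### Paired baseline-to-endpoint tests in a single open-label arm are set as the test of a drug effect, which they cannot isolate; the plan should estimate response and change with confidence intervals instead

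*Combined protocol and SAP*

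**What the plan says.** The Statistical Analysis Plan opens with "Change from baseline will be analyzed statistically to test the main study hypotheses". It gives the hypothesis as "Onfi® has a dual role of improving both behavioral/psychiatric status, namely anxiety symptoms, as well as seizure control, in patients with epilepsy". The primary outcome is a clinical global improvement rating, covering neurological and behavioral status, with a rating of 1 or 2 on the 7-point scale counted as response. Paired t-tests compare baseline with endpoint for response versus non-response. Paired t-tests are also named for the secondary measures: PARS, MASC and the epilepsy quality-of-life scale.

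The Abstract describes a "prospective open-label clinical trial of 20 children and adolescents with epilepsy". The Overview of Study Design says "This study is an open label, adjunctive, proof of concept, pilot clinical trial", and adds: "All participants will receive active treatment, involving flexible dose titration of clobazam". Participants "will be monitored for a period of four months"; Study Visits puts the period at about four and a half months, with contact every two weeks.

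The Inclusion criteria require a subscale score above the age and gender norm on PARS or MASC. The documents name no concurrent or historical control, benchmark response rate, anxiety run-in or blinded rater. Nothing in them says that the baseline-to-endpoint result will be read as descriptive.

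**The concern.** The hypothesis is causal: the drug improves two conditions. The null hypothesis of a paired baseline-to-endpoint test is that the mean does not change over the study period. The two coincide only if nothing except clobazam can move the scores. Here several other things can:

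- **Natural course** of anxiety and seizures over about four months.
- **Expectation**, since families and raters know the treatment and the primary outcome is a global judgment.
- **Frequent contact**, with mental health status assessed every two weeks.
- **Regression to the mean**. Children enter partly because a PARS or MASC score is high, and the same scales are outcomes. Study Visits treats the screening visit as the baseline visit, so the selecting score may also be the reference score.

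Followed as written, the plan can credit an inert drug with a dual benefit. The chance of that is governed by the size of the non-drug change, not by the alpha chosen for the test.

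**Working it through.** **Inputs from the documents.** n = 20 (Abstract); one arm, all treated (Overview of Study Design); paired t-tests and a responder definition of CGI-Improvement 1 or 2 (Statistical Analysis Plan); entry on above-norm PARS or MASC (Inclusion criteria). The documents give no alpha, power, effect size, SD, expected response rate or dropout, so there is no planned figure to reproduce.

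**Assumptions.** Two-sided alpha 0.05, all 20 analyzed, zero drug effect. Non-drug change, non-drug response rate, test-retest correlation and entry cut-off are assumed and shown as ranges.

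**1. Continuous paired change.** The critical value is t(0.975; 19 df) = 2.093, so a standardized mean change of 2.093/√20 = 0.47 is significant. If the true non-drug improvement is d SDs of change, t follows a noncentral t distribution with 19 df and noncentrality d√20. The chance of a significant result in the improvement direction is P(t > 2.093):

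| d (assumed) | d√20 | Significant improvement, inert drug |
|---|---|---|
| 0 | 0 | 2.5% |
| 0.1 | 0.447 | 6% |
| 0.2 | 0.894 | 13% |
| 0.3 | 1.342 | 25% |
| 0.5 | 2.236 | 56% |
| 0.7 | 3.130 | 84% |

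These figures apply to the secondary scale scores, not to the primary responder variable.

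**2. Primary responder variable.** CGI-Improvement has no value at baseline, so the named test needs an interpretation. Here every baseline is scored 0 (non-response) and every endpoint 0 or 1. With k responders, p = k/20, the SD of the differences is √(20p(1−p)/19) and t = p/(SD/√20).

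- k = 3: t = 0.15/0.0819 = 1.83, p = 0.083.
- k = 4: t = 0.20/0.0918 = 2.18, p = 0.042.

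Four responders of 20 therefore suffice. The chance of at least 4 with an inert drug is the binomial tail P(X ≥ 4; 20, π), where π is the assumed non-drug response rate: 13% for π = 10%, 59% for 20%, 89% for 30%.

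**3. Regression to the mean alone.** Simulation at n = 20: bivariate normal scores, no true change, entry above a cut-off on the baseline score, test-retest correlation r. Share of trials with significant improvement:

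| r (assumed) | Entry above the mean | Entry at least 1 SD above |
|---|---|---|
| 0.9 | 12% | 32% |
| 0.8 | 19% | 57% |
| 0.7 | 28% | 76% |
| 0.6 | 37% | 88% |

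The documents do not say how far above the norm a score must lie, so both columns are illustrations. They apply to a scale on which selection was actually made.

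**4. Is a controlled test feasible at this size?** With a 1:1 control, two-sided 0.05, 80% power and an assumed 30% versus 60% response, about 42 patients per arm are needed. Ten per arm gives about 26% power. A confirmatory comparison is therefore out of reach at N = 20, and estimation is the realistic aim. With 10 responders of 20, for example, the estimate is 50% with an exact 95% interval of 27% to 73%.

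**The case against.** The study is openly labeled a proof-of-concept pilot, and a single arm is an ordinary choice for one. Testing change from baseline to look for a signal is not in itself contradictory. That stands: the fault lies in what the test is said to establish, not in the lack of a control arm.

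The plan also states no alpha, no success rule and never speaks of statistical significance, so the error rates above rest on the ordinary reading of a t-test used to test a hypothesis. That stands as a limit on the figures. So does the lack of a source for the size of non-drug change: at 0.1 SD the inflation is small.

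Some safeguards exist. The Inclusion criteria ask for a 60-day seizure baseline, 30 days of stable anticonvulsants and no recent clusters or status epilepticus. The Exclusion criteria rule out current antidepressants and standing benzodiazepines. These help for seizures at entry, but provide no comparison, no anxiety run-in and no rule on background treatment after entry.

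A reader might go further and infer that a significant pre-post result is to be reported as showing clobazam superior to other treatment, because the Abstract speaks of a drug "which may represent a more effective and better tolerated treatment option for the numerous patients with seizure disorders who also have anxiety" and of findings that "potentially will make an immediate clinical impact". The documents do not support that. Both phrases are hedged rationale, and the Statistical Analysis Plan makes no comparative claim and ties neither phrase to a test.

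**Conclusion.** The point holds for the Statistical Analysis Plan's framing: tests of change over time are presented as tests of a drug effect, and no section limits the interpretation. At n = 20 and an assumed two-sided 0.05, every assumed non-zero non-drug change examined lifts the false-improvement rate above 2.5%, from 6% at 0.1 SD to 84% at 0.7 SD. On the all-non-response reading of baseline, the primary test would favor an inert drug in 59% or 89% of trials at an assumed 20% or 30% non-drug response rate. The direction follows from the design; the sizes depend on the assumptions. It would be too strong to say that the plan contradicts its pilot label or breaches an error rate it has set, since it sets none.

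**What to change.** Reword the Statistical Analysis Plan in two places.

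1. **Objective.** Make the primary objective to estimate, under open-label adjunctive clobazam, the CGI-Improvement response proportion with an exact 95% confidence interval. Report mean change on PARS, MASC and quality of life with 95% confidence intervals. This matches the proof-of-concept pilot label.
2. **Interpretation.** State that any p-value describes change over time under open-label treatment and will not be reported as evidence of drug efficacy. Name natural course, expectation, frequent contact and regression to the mean as reasons.

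The cost is SAP text and a more modest claim. Participants, visits and outcome measures are unchanged. The Abstract's hedged wording is background and needs no change for this fix.

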## **Study Visits**

After initial telephone contact and pre-screening is completed, the screening study visit will be scheduled. At that visit, study details will be reviewed and informed consent will be obtained by the PI. The screening study visit will include detailed medical and psychiatric history review, pertinent, physical examination (vital signs, neurologic exam), and assessment including semi-structured diagnostic interviews and rating scales.

Following the screening visit, participants who qualify and continue consent will enter into the active treatment phase of the study. The initial treatment phase will begin with a dispensing visit. It is expected that the dispensing visit may occur on the same day as the screening visit. However, if it does not occur on the day of the screening visit, it may occur within two weeks of the screening visit.

Continued contact with research participants will be done at regular intervals over a period of approximately 4 ½ months. In-person visits will occur biweekly for the first six weeks. In-person visits will occur monthly for the next two months. A total of seven in-person visits will occur including the baseline or screening visit. Participants who will continue on the drug, managed by their primary clinician, may have their care transitioned to their primary clinician before the time frame of the seventh in-person study visit.

At each contact, inquiry regarding adverse events, physical and mental health status, and compliance with treatment will take place. Safety assessment including mental health status and seizure diary review will take place at each subject contact. Safety assessment will include assessment of suicidal thoughts or actions. The PI will be involved with safety assessment at all study visits for each participant.

Telephone contacts will also be arranged at weeks 8, 12 and 16 to assess safety, adverse events and tolerability. Subject contact will occur every two weeks for the duration of the study.

All participants will receive adjunctive clobazam as active treatment. Initial titration will occur at standard dosage schedules, expected to be 5-10mg daily with 5-20mg biweekly increases. Increases may progress to a total of 40 mg daily, either in single dosages or divided dosages. Mimicking clinical practice, a flexible dose paradigm will be utilized to allow titration to effect and mitigation of

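### The plan reads an unblinded, single-arm CGI-Improvement response as a test of a dual drug effect; the design can only estimate change during open-label clobazam

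*Combined protocol and SAP*

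**What the plan says.** All references are to the combined protocol and SAP.

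- **Design.** Overview of Study Design: "This study is an open label, adjunctive, proof of concept, pilot clinical trial". The Abstract gives the size: "prospective open-label clinical trial of 20 children and adolescents with epilepsy". Study Visits confirms that there is no comparator: "All participants will receive adjunctive clobazam as active treatment".
- **Dosing.** Study Visits: "a flexible dose paradigm will be utilized to allow titration to effect".
- **Aim.** The Statistical Analysis Plan says that change from baseline will be used to "test the main study hypotheses--that Onfi® has a dual role of improving both behavioral/psychiatric status", with seizure control as the other half of the claim.
- **Primary outcome.** The same section takes global improvement from baseline as the primary variable. It covers neurological status (including seizures) and behavioral status, and is dichotomised: "CGI-Improvement ratings of a 1 or 2 (on a 7 point scale) will be considered positive responses". Response versus non-response is compared between baseline and endpoint by paired t-test. No alpha, sidedness or reference response rate is given.
- **Other measures.** PARS, MASC and the Quality of Life in Epilepsy Scale are secondary outcomes, each with its own paired t-test. The seizure diary is reviewed at each contact as part of safety assessment (Study Visits), and a 60-day seizure baseline is required (Inclusion criteria). Neither appears in the analysis plan.
- **Rater.** No section says who rates the CGI, when it is rated relative to dose decisions, or whether the rater is independent. The nearest statement concerns safety: "The PI will be involved with safety assessment at all study visits for each participant".

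**The concern.** The primary endpoint is a judgement of benefit made with full knowledge that the child is on clobazam. Because it is cut between 2 and 3, a lift of one category turns a non-responder into a responder. In a randomised comparison, part of such optimism would appear in both arms and cancel. Here there is no second arm, so rater optimism, spontaneous improvement and regression to the mean all enter the response rate as if they were drug effect. Regression to the mean is a live possibility because children are selected for elevated anxiety scores.

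An uncontrolled pilot can live with this if it reports what it observed. This plan goes further and treats the result as a test of whether the drug improves both conditions. At stake is the conclusion itself: a small p-value would be read as evidence of a dual effect when the test addresses a different and much weaker question.

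**Working it through.** The plan states no power, alpha, expected response rate or sample-size derivation, so it has no figure to reproduce. The check asks what the planned test would declare, and under what conditions.

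**Inputs from the documents:** n = 20 (Abstract); response = CGI-Improvement 1 or 2, compared by paired t-test (Statistical Analysis Plan).

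**Assumptions:** two-sided alpha 0.05. Every child is coded 0 (non-response) at baseline, because an improvement scale has no baseline value of its own and the plan does not say what to use. All 20 children are rated at endpoint.

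**Step 1: how many responders the test needs.** With baseline all 0, the paired difference is 1 for responders and 0 otherwise. With k responders and r = k/n, the mean is r and the sample variance is [n/(n−1)]·r(1−r), so

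t = √[(n−1)·r/(1−r)], on 19 degrees of freedom.

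- k = 3, r = 0.15: t = √(19 × 0.15/0.85) = 1.83, p = 0.083.
- k = 4, r = 0.20: t = √(19 × 0.20/0.80) = 2.18, p = 0.042.

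Four responders in 20 are enough. The null hypothesis rejected is that the mean response is zero, meaning that no child would ever be rated 1 or 2. That is not the hypothesis that the drug has no effect.

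**Step 2: how often a drug with no effect would pass.** Let q be the probability that a child is rated 1 or 2 for reasons other than the drug. With X ~ Binomial(20, q), P(X ≥ 4) = 1 − P(X ≤ 3):

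| q (assumed) | P(X ≤ 3) | P(X ≥ 4) |
|---|---|---|
| 0.10 | 0.867 | 13% |
| 0.20 | 0.411 | 59% |
| 0.30 | 0.107 | 89% |

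**Step 3: inflation of the response rate (illustration only).** If the true response rate is p and a share f of true non-responders is rated across the cut, the expected observed rate is p + f(1−p). This allows upward misrating only.

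- p = 0.30, f = 0.10: 0.30 + 0.10 × 0.70 = 0.37, or 7.4 of 20.
- p = 0.30, f = 0.25: 0.30 + 0.25 × 0.70 = 0.475, or 9.5 of 20.
- p = 0.50, f = 0.10 to 0.25: 0.55 to 0.625.

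At p = 0.30 the expected count rises from 6 to between 7.4 and 9.5. Neither p nor f comes from the documents.

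**Step 4: what an interval would show.** For 4 of 20, the exact (Clopper–Pearson) 95% limits are the 0.025 quantile of Beta(4, 17) and the 0.975 quantile of Beta(5, 16): 5.7% to 43.7%. This describes sampling uncertainty honestly and claims nothing about cause. It does not correct for bias.

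**The case against.** The strongest reply is that the plan conceals nothing. It declares itself open label, proof of concept and a pilot, and the lack of a control arm follows from that choice. Three further scales are prespecified, so a CGI result at odds with them would be visible. The bias figures are assumed, and the plan sets no success threshold that they could be shown to cross. All of this stands. It is why the point is about the claim attached to the result, not the choice of design, and why the 37–48% range is illustrative.

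A reader might infer more: that the clinician who sets the dose also rates the outcome, that both judgements are made at the same visit, or that the PI is the rater. The documents do not support this. They name neither the CGI rater nor the person who sets the dose and give no CGI schedule beyond baseline and endpoint. The statement about the PI concerns safety assessment. What can be said is that no independent rater and no separation of rating from dosing is specified.

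A reader might also want a positive conclusion to require agreement between the CGI and the questionnaires, as informants free of rater bias. The documents do not say who completes the MASC or the quality-of-life scale, and every respondent is equally unblinded. Shared expectation could produce agreement, so a concordance gate would be weak protection.

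**Conclusion.** The point holds for the inference drawn from the primary outcome. In a single-arm, unblinded trial, the planned test of CGI-Improvement response cannot show that the drug improves anxiety and seizure control. With baseline coded as non-response and two-sided alpha 0.05, it is nominally significant from 4 responders in 20. Causes other than the drug could produce that count with probability from 13% to 89% if they yield a rating of 1 or 2 in 10% to 30% of children.

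These figures depend on the baseline coding, the alpha and the assumed rates, none of which the plan states. The size of any rater bias is unknown, and the documents do not show that bias will occur. The conclusion does not depend on its size: a test against a zero response rate, without a comparator, does not isolate drug effect whatever the bias. It is also not shown that rating and dosing are in the same hands.

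**What to change.** In the Statistical Analysis Plan:

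1. Replace the test of the dual-role hypothesis with estimation of change during open-label adjunctive clobazam.
2. Report the proportion with CGI-Improvement 1 or 2 with an exact 95% confidence interval, described as an unblinded impression, in place of the paired t-test on response.
3. Present it beside the changes in PARS, MASC and quality of life, and beside diary seizure counts compared with the 60-day baseline. State any disagreement in the text. Do not make agreement a condition for reporting.

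Optionally, record the CGI after the diary review, since the rating must reflect seizure control, but before any dose decision at that visit, with the same rater for a given child throughout. This limits contamination by the dose decision. It does not remove expectation, because the rater still knows the treatment.

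The cost is revised SAP wording, one tabulation of diary data already collected and, for the optional step, a reordered visit worksheet. No staff, visits or participants are added. The downside is a less favourable claim: the trial would report change during treatment, not a demonstrated dual effect.

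### The primary analysis cuts the 7-point CGI-Improvement rating to response versus non-response and plans no analysis of the full rating, so slight improvement, no change and worsening cannot be told apart

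*Combined protocol and SAP*

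**What the plan says.** All of the analysis text is in the section Statistical Analysis Plan.

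- Primary outcome: "The primary outcome variable will be Clinical Global Assessment of Functioning Improvement from baseline". The rating is meant to reflect both seizure control and behaviour.
- Cut: "CGI-Improvement ratings of a 1 or 2 (on a 7 point scale) will be considered positive responses". By implication, 3 to 7 is non-response.
- Primary test: "Paired student's t-tests will be used to compare baseline and study endpoint ratings for response versus non-response".
- Secondary scales (PARS, MASC, quality of life): "Paired student's t-tests will be used to compare baseline and study end outcomes for each measure". A positive-outcome cut is defined for these as well, but none of them is the global rating.

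The Abstract gives the size, a "prospective open-label clinical trial of 20 children and adolescents with epilepsy", and Overview of Study Design gives the setting: "This study is an open label, adjunctive, proof of concept, pilot clinical trial". All participants receive clobazam. The document states no alpha, sidedness, power, SD, expected or null response rate, and gives no reason for analysing the cut rather than the rating.

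**The concern.** Pooling 3 to 7 gives a child rated 3 the same value as a child rated 7. Nine responders with eleven children rated 4, and nine responders with eleven rated 6 or 7, give the same primary result: 9/20 = 45%. Those are different findings about an adjunctive psychoactive drug in children with epilepsy. No other planned analysis of the global rating would tell them apart.

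The second cost is statistical. A pilot of 20 has little information to spare, and a two-level version of a seven-level rating carries less of it. How much less depends on what the planned test is taken to be, so the two readings have to be kept apart.

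**Working it through.** There is no power figure in the plan to reproduce. The sample size (20), the scale (1 to 7) and the cut (1 or 2) come from the documents. Everything else below is assumed.

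**1. The test read literally.** An improvement rating has no baseline value. If response is coded 0/1 and every child is 0 at baseline, the paired t-test is a one-sample t-test of the response indicator against zero. With k responders, p̂ = k/20 and t = p̂ / √[p̂(1 − p̂)/19].

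- k = 3: t = 0.15 / √(0.1275/19) = 1.83, two-sided p = 0.083.
- k = 4: t = 0.20 / √(0.16/19) = 2.18, two-sided p = 0.042.

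Four responders therefore suffice at an assumed two-sided 5%. The chance of 4 or more of 20 is 59%, 89% and 98% at true response rates of 20%, 30% and 40%, so power is not low. The null, however, is that nobody would ever be rated 1 or 2. Take a normal rating centred on 4 and rounded to 1–7, so that P(rating ≤ 2) = Φ((2.5 − 4)/SD):

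| SD | P(rating ≤ 2), no shift from 4 | P(4 or more of 20) |
|---|---|---|
| 1.0 | 0.067 | 4% |
| 1.2 | 0.106 | 15% |
| 1.5 | 0.159 | 39% |

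**2. A binary test with controlled error against a full-scale test.** The binary test is an exact binomial test of the response count against the null rate Φ((2.5 − μ₀)/SD), at one-sided 2.5%. The full-scale test is a one-sample t-test of the 1–7 rating against μ₀, by simulation. The binomial count is discrete, so its actual alpha lies below 2.5%. For a fair comparison the t-test is run at that same alpha.

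| SD | μ₀ | True mean | Critical count | Actual alpha | Binary power | Full-scale power, same alpha | Difference (points) |
|---|---|---|---|---|---|---|---|
| 1.0 | 4.0 | 3.2 | 5 | 0.009 | 55% | 79% | 24 |
| 1.2 | 4.0 | 3.2 | 6 | 0.015 | 50% | 71% | 20 |
| 1.2 | 4.0 | 3.0 | 6 | 0.015 | 72% | 89% | 17 |
| 1.5 | 4.0 | 3.0 | 8 | 0.008 | 47% | 63% | 16 |
| 1.5 | 4.0 | 2.7 | 8 | 0.008 | 74% | 87% | 13 |
| 1.2 | 3.3 | 2.5 | 10 | 0.015 | 59% | 71% | 12 |
| 1.5 | 3.3 | 2.5 | 11 | 0.016 | 41% | 50% | 8 |

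Differences are taken before rounding. With the t-test at a full 2.5%, the five μ₀ = 4 rows give 90%, 79%, 93%, 80% and 95%; part of that larger gap is only the unequal alpha. A simulated signed-rank test at 2.5% gives 90%, 79%, 92%, 78% and 93% in those rows, so the t-test is a fair stand-in for it.

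**3. What a test against no change would pick up.** Suppose the mean is 3.3 through non-drug improvement alone. For SD 1.0, 1.2 and 1.5, the one-sample t-test against 4 rejects 82%, 68% and 50% of the time (signed-rank 80%, 67% and 48%). The literal paired test rejects 64%, 78% and 89%. The exact binomial test calibrated to μ₀ = 4 rejects 42%, 39% and about 21%.

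**The case against.** - **Power.** A reader might infer that the cut leaves the planned trial short of power. The documents do not support that. They state no power and no binomial test, and the paired t-test as literally written rejects too often rather than too rarely. The loss appears only once that test is replaced by one with a controlled error rate, and its size then rests on assumptions. This objection stands and limits the claim.
- **Ambiguity.** The word for ratings in the test sentence could mean the scores themselves. That is possible, but the reference to response versus non-response would then have no role, and an improvement score still has no baseline value to pair with. The wording needs repair on either reading.
- **Uncontrolled improvement.** In an open-label single-arm study, a test against no change also detects placebo response, rater expectation and natural improvement, and more readily than a calibrated binary test does (step 3). This stands as a limit on interpretation. It does not favour the present text, whose literal test rejects 64% to 89% of the time in the same settings.
- **Context.** This is a proof-of-concept pilot, the secondary scales are compared with baseline, and adverse events and health status are reviewed at every contact (Study Visits). Worsening is therefore not invisible to the trial. None of this recovers the distribution of the global rating, which is the primary outcome.

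**Conclusion.** The loss of distinction among ratings 3 to 7 follows from the text and needs no assumptions beyond the usual labels for those categories. The test sentence is ambiguous, and on its literal reading its fault is a null of zero response, with false positives of about 4% to 39% under the assumed SDs.

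For any replacement with a controlled error rate, keeping only the cut costs roughly 8 to 24 points of power for moderate effects. That range assumes n = 20 with no dropout, a rounded normal rating, SD 1.0 to 1.5, a null mean of 4 or 3.3, and equal actual alpha. The documents supply none of these except the 20, so the range is illustrative and the loss is smaller when both tests are near full power.

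The change is worth making because it is cheap. It does not turn the study into evidence of a drug effect.

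**What to change.** In the Statistical Analysis Plan section:

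1. Replace the paired t-test on response with a one-sample test of the full endpoint CGI-Improvement rating against the no-change midpoint (Wilcoxon signed-rank), reported with the mean and 95% CI. State the scale labels, including which value means no change.
2. Keep a rating of 1 or 2 as the responder definition and report it as a proportion with an exact 95% CI. For example, 10 of 20 gives 27% to 73%.
3. Tabulate all seven categories, so that worsening is visible.
4. Describe the result only as change on treatment, and say that without a control arm it may include placebo response, rater expectation and natural improvement.

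The cost is a few sentences, with no new data, visits or participants. There are three downsides to state. The p-value then refers to average change and not to the responder definition. The signed-rank test uses the spacing of an ordinal scale. And the test rejects about 50% to 82% of the time if the mean is 3.3 with no drug effect.
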